8.4 Data Monitoring Committee

A DMC will review cumulative safety data at scheduled meetings. Of note, the clinical safety plan for this study includes close monitoring by the investigator for signs of abnormal cardiac and hepatic parameters, study entry criteria and treatment discontinuation criteria (Section 5.6).

The collection and summary of these data will be prepared by a designated CRO or Novartis.

Details on the organization and function of the DMC will be described in the DMC charter.

8.5 Adjudication Committee

An adjudication committee will be used to adjudicate rescue therapy and concomitant medication that might have an impact on the primary endpoint. Blinded adjudication of rescue therapy and concomitant medication will be implemented for the final data base lock by considering factors such as the type of medication, indication, timing, frequency and the potential impact of the use. Details regarding the adjudication process will be available in the relevant Adjudication Committee charter.

In addition, an adjudication committee might be used to monitor specific safety events, including, but potentially not limited to, clinically significant cardio- and liver events. The events would be blindly reviewed and adjudicated as they occur during the conduct of a trial. Details regarding the adjudication process would be available, as needed, in the relevant Adjudication Committee charter.

9 Data analysis

The analysis will be conducted on all subject data at the time the trial ends. Any data analysis carried out independently by the investigator should be submitted to Novartis before publication or presentation.

Summary statistics for continuous variables will include N, mean, standard deviation, minimum, lower quartile, median, upper quartile, maximum. Summary statistics for discrete variables will be presented in contingency tables and will include absolute and relative frequencies. If not otherwise specified, p-values will be presented as two-sided p-values and two-sided confidence intervals will be displayed.

9.1 Analysis sets

Randomized Set: All subjects randomized are included in the Randomized Set. Subjects will be analyzed according to the treatment assigned to at randomization.

Full Analysis Set (FAS): The FAS comprises all subjects to whom study treatment has been assigned. Following the intent-to-treat principle, subjects will be analyzed according to the treatment assigned to at randomization. Mis-randomized subjects (mis-randomized in IRT) will be excluded from FAS. Mis-randomized subjects are defined as cases where IRT contacts were made by the site either prematurely or inappropriately prior to confirmation of the subject's final randomization eligibility and no study medication was administered to the subject.

Safety Set: The Safety Set includes all subjects who received at least one dose of study medication. Subjects will be analyzed according to treatment received.

9.2 Subject demographics and other baseline characteristics

Analyses will be based on the Randomized Set.

Demographics and baseline characteristics

Summary statistics will be presented for continuous demographic and baseline characteristic variables for each treatment group. The number and percentage of subjects in each category will be presented for categorical variables for each treatment group and all subjects.

Medical history

Disease-specific medical history and any condition entered as medical history or current medical conditions at baseline will be coded using the MedDRA dictionary. They will be summarized by system organ class and preferred term of the MedDRA dictionary.

9.3 Treatments

Analyses of treatment will be based on the Safety Set.

Study treatment

The duration of exposure to study treatment will be summarized by treatment group. In addition, the number of subjects with exposure of at least certain thresholds (e.g., any exposure, ≥ 1 week, ≥ 2 weeks, ≥ 3 weeks, ≥ 4 weeks, ≥ 6 weeks, ≥ 8 weeks, etc.) will be displayed.

Prior and concomitant medication

Prior and concomitant medications will be summarized by treatment separated for AD related and non-AD related medications. AD-related concomitant medications will be summarized by pre-specified categories, route of administration and preferred term. Non-AD related concomitant medications will be summarized by the preferred term.

Rescue therapy (duration of use and amount used) will also be summarized.

9.4 Analysis of the primary variable(s)

All analyses for efficacy data will be based on the FAS.

The primary objective of this study is to characterize the dose response relationship among ZPL389 doses (3, 10, 30 and 50 mg o.d.) and placebo with respect to achievement of IGA response after 16 weeks of treatment, and to select an appropriate dose (or range of doses) to use in Phase 3 studies. The consecutive steps are therefore (1) to confirm an overall dose-response signal, (2) to estimate the minimal ZPL389 dose that shows a relevant effect based on the selected dose response model. The Multiple Comparison Procedures – Modelling (MCP-Mod) methodology (Bretz, et al 2005, Pinheiro, et al 2014, Qualification Opinion on MCP-Mod EMA 2014, FDA endorsement 2015) will be used to address these goals.

9.4.1 Primary Variable(s)

The primary variable for the study is IGA response after 16 weeks of treatment.

IGA response is defined as achievement of an IGA score of 0 or 1 with a 2-point reduction from baseline and no use of confounding therapy as adjudicated up to the assessment time point.

9.4.2 Statistical model, hypothesis, and method of analysis

The null hypothesis of a constant dose-response curve for the primary efficacy endpoint will be tested at a significance level of 5% against the one-sided alternative hypothesis of a nonconstant dose response curve using the MCP-Mod methodology.

A logistic regression model will be fitted with response as outcome variable and treatment (dose as categorical variable) and baseline IGA as covariates.

The response Y_{ij} for subject *j* in dose group *i* receiving dose d_i is modelled as $Y_{ij} \sim Bin(1, p_{ij})$ with $p_{ij} = logit^{-1}(\delta_i + \mathbf{x}_{ij}; \boldsymbol{\beta}), i=1,...,5, j=1,..., n_i$

where Bin(1,*p*) denotes the binomial distribution with parameter 1 and *p*, δ_i is the effect of dose d_i , β refers to the vector of regression coefficients corresponding to additional covariates x_{ij} which represent the baseline IGA category. Finally, n_i is the number of subjects allocated to each treatment group. If the covariate baseline IGA prevents fitting of a model, it will be dropped.

Population-average estimates of the logit of the response probability for each dose will be derived based on the results of the logistic regression. This will be a weighted sum of the corresponding estimates for each baseline IGA. The weights will be based on the observed frequencies of the baseline IGA category in the FAS.

The covariance matrix of the estimates will also be estimated based on the logistic regression results. Using the obtained estimates and estimated covariance matrix generalized MCP-Mod (Pinheiro 2014) will be performed.

The following dose-response shapes are selected as candidates:

- 1. Sigmoid Emax model (with fixed Hill parameter): $f(d, \theta) = E0 + Emax^*dh/(dh + ED50h)$
- sigEmax1: ED50 = 25 mg, Hill parameter = 4.0
- sigEmax2: ED50 = 30 mg, Hill parameter = 8.0
- sigEmax3: ED50 = 1.85 mg, Hill parameter = 3.0
- sigEmax4: ED50 = 7.5 mg, Hill parameter = 5.0
- 2. Emax model: $f(d, \theta) = E0 + Emax*d/(d+ED50)$
- Emax1: ED50 = 15 mg
- Emax2: ED50 = 45 mg
- 3. beta model: E0+Emax*B($\delta 1$, $\delta 2$)*x^{$\delta 1$}(1-x)^{$\delta 2$} with x=d/scale
- Scale=71, δ1=1.1, δ2=1.1

Figure 9-1Candidate models for IGA response at Week 16

For each candidate model a contrast test statistic, based on a linear combination of the treatment estimates per dose will be derived. The contrast coefficients will be chosen to maximize the power to detect the pre-specified candidate models. The global test decision is based on the maximum of the contrast test statistics. A critical value q controlling the type I error rate can be derived from the fact that the contrast test statistics approximately follow a multivariate normal distribution and that their maximum follows the distribution of the maximum of a multivariate normal distribution. If the maximum contrast test statistic exceeds the critical value q, the overall null hypothesis of a constant dose-response curve is rejected and one proceeds to the further estimation steps to determine the dose-response curve and doses achieving target clinical effects using a dose-response model.

Bootstrap model averaging will be used to estimate the dose-response curve, the target dose and to derive confidence intervals. Bootstrap simulation will be performed using the multivariate normal distribution of the estimates of the logit of the response probability for each dose and generalized least-squares fitting of the resulting simulated values (see Pinheiro et al. 2014). The target dose is defined as the dose for which the expected response rate is at least 15% higher than the response rate of placebo which is expected to be about 10%. This will be based on the estimated dose-response curve.

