9.5 Analysis of secondary variables

9.5.1 Efficacy variables

All analyses will be based on the FAS if not specified otherwise. For handling of missing data refer to Section 9.4.3.

Percent change from baseline EASI score at Week 16

The null hypothesis of a constant dose-response curve for the EASI score will be tested at a significance level of 5% against the one-sided alternative hypothesis of a non-constant dose response curve using the MCP-Mod methodology (Bretz, et al 2005, Pinheiro, et al 2014, Qualification Opinion on MCP-Mod EMA 2014, FDA endorsement 2015), in analogy to the primary endpoint analysis.

To allow adjustment for correlations between time points within subjects, a mixed effect model for repeated measurements (MMRM) approach is adopted to obtain the least squares means fits.

The mean responses at each individual dose will be obtained through covariate-adjusted treatment effects by modeling the primary efficacy variable using MMRM. The model will contain treatment group, baseline EASI score, geographical region, baseline IGA score, visit, baseline EASI score*visit, and treatment group*visit as covariates, with unstructured covariance matrix.

The covariance matrix of the estimates will also be estimated based on the MMRM results. Using the obtained estimates and estimated covariance matrix generalized MCP-Mod (Pinheiro 2014) will be performed.

The following dose-response shapes are selected as candidates:

- 1. Sigmoid Emax model (with fixed Hill parameter): $f(d, \theta) = E0 + Emax d^h/(d^h + ED50^h)$
- sigEmax1: ED50 = 25 mg, Hill parameter = 4.0
- sigEmax2: ED50 = 30 mg, Hill parameter = 8.0
- sigEmax3: ED50 = 1.85 mg, Hill parameter = 3.0
- sigEmax3: ED50 = 7.5 mg, Hill parameter = 5.0
- 2. Emax model: $f(d, \theta) = E0 + Emax*d/(d+ED50)$
- emax1: ED50 = 15 mg
- emax2: ED50 = 45 mg
- 3. beta model: E0+Emax*B($\delta 1$, $\delta 2$)*x^{$\delta 1$}(1-x)^{$\delta 2$} with x=d/scale
- beta1: Scale=71, δ 1=1.1, δ 2=1.1

Figure 9-2 Candidate models for percent change from baseline EASI score at Week 16

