For each candidate model a contrast test statistic, based on a linear combination of the treatment estimates per dose will be derived. The contrast coefficients will be chosen to maximize the power to detect the pre-specified candidate models. The global test decision is based on the maximum of the contrast test statistics. A critical value q controlling the type I error rate can be derived from the fact that the contrast test statistics approximately follow a multivariate normal distribution and that their maximum follows the distribution of the maximum of a multivariate normal distribution. If the maximum contrast test statistic exceeds the critical value q, the overall null hypothesis of a constant dose-response curve is rejected and one proceeds to the further estimation steps to determine the dose-response curve and doses achieving target clinical effects using a dose-response model.

Bootstrap model averaging will be used to estimate the dose-response curve and to derive confidence intervals. Bootstrap simulation will be performed using the multivariate normal distribution of the parameter estimates and generalized least-squares fitting of the resulting simulated values.

IGA score

Summary tables will be presented by treatment group and visit which include absolute and relative frequencies. Shifts from baseline IGA score will also be summarized by visit.

IGA/EASI50/EASI75 response

Summary tables will be presented by treatment group and visit which include absolute and relative frequencies. Time courses of the estimated response rate including 95% confidence interval will be plotted for each treatment group. For pairwise comparisons between treatment groups (individual ZPL389 arms versus placebo),

- odds ratios and 95% confidence intervals will be derived using logistic regression with treatment group, baseline IGA and geographical region as covariate
- the individual rate differences of the active treatment groups to placebo and the respective 95% confidence intervals will be derived using a normal approximation.

EASI score as well as absolute and percent change from baseline EASI score

Summary statistics will be presented by treatment group and visit.

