9.8 Sample size calculation

The primary objective of this study is to characterize the dose response relationship among ZPL389 doses (3, 10, 30 and 50 mg o.d.) and placebo with respect to achievement of IGA response after 16 weeks of treatment. The sample size was determined with the software ADDPLAN DF, version 3.1.8, with settings for minimum power function and model based contrasts.

The sample size is derived to detect a dose-response with 90% power and a one-sided alpha of 2.5%. Based on literature data Simpson et al 2017, a placebo response rate of 10% is assumed. A maximum treatment effect for ZPL389 of 20%-points higher than placebo is assumed. An

unbalanced allocation ratio of 2:1:1:2:2 corresponding to treatment arms placebo: 3 mg: 10 mg: 30 mg: 50 mg, with more subjects allocated to placebo and the higher doses, is chosen to increase the precision of the estimate for the treatment effect at doses in the expected efficacious dose range.

Under these assumptions, a sample size of 360 subjects in total will be required, randomized to 90:45:45:90:90 subjects corresponding to placebo: 3 mg: 10 mg: 30 mg: 50 mg treatment arms.

In order to show consistency of the treatment effect in Japanese subjects compared to the non-Japanese population, it was estimated that approximately 40 Japanese subjects need to be recruited, i.e. the trial will include approximately 320 non-Japanese subjects and 40 Japanese subjects and the total sample size is 360 subjects.

10 Ethical considerations

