# 2 Statistical methods

# 2.1 Data analysis general information

Novartis will perform the analyses for this study. Statistical software SAS verion 9.4 or later will be used.

All available data from the core and extension studies will be presented together.

Where summary statistics are presented these will include, for continuous variables N, mean, standard deviation, minimum, and maximum, and for discrete variables, counts and appropriate percentages.

If not otherwise specified, p-values will be presented for two-sided hypothesis testing, twosided confidence intervals will be displayed and the level of significance will be set to 5% twosided.

In general listings will be presented by treatment sequence showing the sequence of treatments in the core and extension study, i.e as follows and in this order

- Placebo did not participate in extension
- Placebo ZPL389 50mg
- Placebo ZPL389 30mg

- ZPL389 3mg did not participate in extension
- ZPL389 3mg ZPL389 30mg
- ZPL389 3mg ZPL389 50mg
- ZPL389 10mg did not participate in extension
- ZPL389 10mg ZPL389 30mg
- ZPL389 10 mg ZPL389 50mg
- ZPL389 30mg did not participate in extension
- ZPL389 30mg ZPL389 30mg
- ZPL389 50mg did not participate in extension
- ZPL389 50mg ZPL389 50mg

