# 2.5.2 Statistical hypothesis, model, and method of analysis

The key questions to address this objective are

- Is there a dose-response relationship for IGA response after 16 weeks of treatment?
- What is the form of this dose-response?

• What doses deliver sufficient efficacy in terms of IGA response after 16 weeks of treatment?

Results from the interim analysis indicate that there is no dose-response relationship and therefore the second and third questions are no longer relevant. Thus the analysis of the primary variable will focus only on the logistic regression analysis described in the protocol, establishing the presence or absence of a dose-response relationship. The MCP-Mod procedure as outlined in the protocol will not be carried out.

The primary objective will be achieved if the null hypothesis of no difference between treatment groups is rejected at 5% one-sided level.

A logistic regression model will be fitted with IGA response as the outcome variable and treatment (dose as categorical variable) and baseline IGA as covariates.

The response  $Y_{ij}$  for subject j in dose group i receiving dose  $d_i$  is modelled as  $Y_{ij} \sim Bin(1, p_{ij})$  with  $p_{ij} = logit^{-1}(\delta_i + \mathbf{x}_{ij}; \boldsymbol{\beta}), i=1,..., 5, j=1,..., n_i$ 

where Bin(1,p) denotes the binomial distribution with parameter 1 and p,  $\delta_i$  is the effect of dose  $d_i$ ,  $\beta$  refers to the vector of regression coefficients corresponding to additional covariates  $x_{ij}$  which represent the baseline IGA category. Finally,  $n_i$  is the number of subjects allocated to each treatment group. If the covariate baseline IGA prevents fitting of a model, it will be dropped.

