# 3 Sample size calculation

The planned sample size for the core study was 360 subjects. Since the study was stopped early the final sample size will be less than this.

The sample size was determined with the software ADDPLAN DF, version 3.1.8, with settings for minimum power function and model based contrasts.

The sample size was derived to detect a dose-response with 90% power and a one-sided alpha of 2.5%. A placebo response rate of 10% was assumed. A maximum treatment effect for ZPL389 of 20%-points higher than placebo wass assumed. An unbalanced allocation ratio of 2:1:1:2:2 corresponding to treatment arms placebo: 3 mg: 10 mg: 30 mg: 50 mg, with more subjects allocated to placebo and the higher doses, was chosen to increase the precision of the estimate for the treatment effect at doses in the expected efficacious dose range.

Under these assumptions, a sample size of 360 subjects in total will be required, randomized to 90:45:45:90:90 subjects corresponding to placebo: 3 mg: 10 mg: 30 mg: 50 mg treatment arms.

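### The trial is sized at one-sided 2.5%, but the primary success threshold is one-sided 5%, and neither document explains the difference

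*Protocol*

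**What the plan says.** **Sizing.** Protocol 9.8: "The sample size is derived to detect a dose-response with 90% power and a one-sided alpha of 2.5" per cent. SAP 3 repeats it: "The sample size was derived to detect a dose-response with 90% power and a one-sided alpha of 2.5" per cent. Both give 360 subjects, 90:45:45:90:90, with a placebo response of 10% and a maximum effect of 20 percentage points.

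**Primary test.** Protocol 9.4.2 sets out an MCP-Mod test of a constant dose-response curve, which "will be tested at a significance level of 5% against the one-sided alternative hypothesis". SAP 2.5.2 drops MCP-Mod, keeps a logistic regression with dose as a categorical factor, and states: "The primary objective will be achieved if the null hypothesis of no difference between treatment groups is rejected at 5% one-sided level".

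**EASI.** Protocol 9.5.1 uses the same level for percent change in EASI: "significance level of 5% against the one-sided alternative hypothesis of a non-constant dose response curve using the MCP-Mod methodology".

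**Default and intervals.** SAP 2.1 provides that, where nothing else is specified, "the level of significance will be set to 5% twosided". Comparisons of each dose with placebo carry two-sided 95% intervals (Protocol 9.5.1: "odds ratios and 95% confidence intervals will be derived using logistic regression"; SAP 2.6.7 for rate differences).

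**Changes.** SAP 4 lists the dropped adjudication and the dropped MCP-Mod analysis. It says nothing about the significance level.

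**The concern.** The level that justifies the sample size is not the level that decides whether the primary objective is met. In the protocol, rejecting the null is the gate to estimating the dose-response curve and the target dose, which feeds the Phase 3 dose choice. A one-sided p-value between 0.025 and 0.05 passes the gate in 9.4.2 but fails at the level used in 9.8. A reader of the final report could not tell from the documents which outcome was planned.

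The SAP adds a second gap. It keeps a formal one-sided criterion but no longer has the test to which the one-sided level belonged.

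**Working it through.** **1. Inputs.** Protocol 9.8: one-sided 2.5%, 90% minimum power over the candidate models, placebo 10%, best dose 30%, n = 90, 45, 45, 90, 90. Protocol 9.4.2: seven candidate shapes (four sigmoid Emax, two Emax, one beta) and analysis on the logit scale. Assumption: each shape is scaled so that its best studied dose moves from 10% to 30%.

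**2. Method.** For dose group i, the variance of the estimated logit is 1/(n_i p_i (1 - p_i)); S is the diagonal matrix of these. The optimal contrast c for a shape with mean vector m is proportional to S^-1 (m - m̄), where m̄ is the S^-1-weighted mean. The statistic is T = c'η̂ / sqrt(c'Sc). The null is rejected if the largest of the seven T exceeds q, the upper 2.5% or 5% point of the multivariate normal maximum (400,000 draws).

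**3. The plan's own figure, and the same test at 5%.** "Size-weighted" means contrasts using S proportional to 1/n_i; the range covers two ways of obtaining q.

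| Quantity | One-sided 2.5% | One-sided 5% |
|---|---|---|
| Critical value q (equal variances, planned n) | 2.32 | 2.02 |
| Minimum power at N = 360, contrasts from each model's covariance | 90.3% | 94.6% |
| Minimum power at N = 360, size-weighted contrasts | 91.7-92.3% | 95.5-95.9% |
| N for 90% minimum power, contrasts from each model's covariance | about 357 | about 296 |

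The stated 360 is reproduced at one-sided 2.5%. The documents do not state the scale or variance used for sizing. Across other choices (probability scale, pooled or fixed variance), N for 90% runs from 261 to 369 at 2.5% and from 215 to 305 at 5%. So the recalculation supports the text of 9.8 but does not replace it. None of the variants gives 360 at one-sided 5%.

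**4. Type I error.** For the MCP-Mod global test, the nominal error equals the level chosen: 5% against 2.5%. Results with 2.02 < max T < 2.32 change sides.

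**5. A single dose-versus-placebo Wald test.** The cut-offs are 1.645 (one-sided 5%) and 1.96 (one-sided 2.5%). Take z = 1.80: one-sided p = 0.036, significant at 5%. The lower 95% limit is (1.80 - 1.96) SE = -0.16 SE, so the interval includes no effect. The two-sided 90% interval, with lower limit (1.80 - 1.645) SE = +0.155 SE, agrees with the one-sided 5% test.

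**6. The SAP test.** SAP 5.2.2 bases p-values on Type III Wald tests. With five dose groups as a factor, that test has four degrees of freedom and no direction, so a one-sided level cannot be attached to it. If the criterion meant any of four unadjusted dose-versus-placebo tests (an assumption, with planned group sizes), the chance of at least one false positive would be about 15.3% at one-sided 5% each and 8.2% at one-sided 2.5% each. The SAP does not say that it means this.

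**The case against.** **The analysis section sets the test level, and it is consistent.** Protocol 9.4.2 and 9.5.1 and SAP 2.5.2 all say 5%. Sizing at a stricter level than the test is conservative, and one-sided 5% can be defended in a dose-finding trial. This stands in part: nothing in the documents proves which figure was intended, and the 90% power is met. But no such reasoning is written down, and the SAP states both levels without linking them.

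**A reader might infer that the 95% intervals contradict the MCP-Mod test and that moving to 2.5% would cure it.** The documents do not support this. MCP-Mod uses a multiplicity-adjusted maximum contrast; the dose-versus-placebo intervals are unadjusted. They do not correspond at either level. In null simulation with the planned group sizes, about 20% of rejections at one-sided 2.5%, and about a third at 5%, have all four pairwise 95% intervals including zero. The interval argument holds only for a single dose-versus-placebo Wald test.

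**A reader might also infer that SAP 2.1 contradicts SAP 2.5.2.** It does not. The two-sided 5% level is a default for cases not otherwise specified, and 2.5.2 specifies otherwise.

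**Practical weight is low.** The study stopped after an interim analysis that, according to SAP 4, showed no treatment effect, and 360 subjects will not be reached. That stands and lowers the priority. The criterion still governs how the final report words the primary result.

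**Conclusion.** The inconsistency is real and appears in both documents: one-sided 2.5% for sizing, one-sided 5% for declaring the primary objective met, with no explanation. The wording of 9.4.2 alone leaves slight room for doubt about sidedness; SAP 2.5.2 removes it.

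For the protocol's MCP-Mod test the consequence is a nominal global error of 5% instead of the 2.5% used for sizing. Power is not reduced; the looser level raises the minimum by about 4 percentage points at N = 360. These power figures rest on logit-scale sizing and the scaling of shapes assumed above.

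It would go too far to say that the final analysis runs at exactly twice the planned false-positive rate. That ratio belongs to the MCP-Mod global test, which the SAP drops. Under the SAP the error rate cannot be stated until the one-sided comparison is named.

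Should-fix, because the early stop for lack of efficacy makes a false-positive claim unlikely in practice.

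**What to change.** 1. In SAP 2.5.2, set the level to one-sided 2.5% and name the contrast or dose-versus-placebo comparison to which it applies, with a multiplicity rule if there is more than one. Record the change in SAP 4.
2. If the protocol is amended, make the same change in 9.4.2 and 9.5.1. This matches 9.8 and SAP 3 and keeps the stated 90% power at the planned 360.
3. If one-sided 5% is kept instead, justify it, restate the power or sample size for that level in Protocol 9.8 and SAP 3, and show two-sided 90% intervals beside the test.

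**Cost.** One figure and a sentence or two in the SAP. The threshold becomes stricter, and the change comes after the May 2020 interim results were seen. It goes in the conservative direction, and the SAP is dated before database lock, so it can be made openly if it is settled before then. Power at the reduced final sample size will be below the planned figure at either level compared with 360 subjects, and the fix cannot recover that.
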